1.0 INTRODUCTION

Heart failure (HF) is a growing epidemic, with 915,000 new cases diagnosed each year, resulting in over 1 million hospitalizations and costs the United States (US) healthcare system over \$30 billion annually¹. Left ventricular assist devices (LVAD) are increasingly being used for treating patients with advanced heart failure as they have demonstrated improved survival over optimal medical management².

Progressively improving outcomes with newer LVAD technology has led to LVAD therapy becoming a mainstay in the treatment of advanced heart failure³, however, LVAD therapy has been beleaguered by hemocompatibility related adverse events – namely thrombosis, stroke and bleeding⁴. Within the prospective randomized multicenter MOMENTUM 3 clinical trial, the HeartMate 3 (HM3) Left Ventricular Assist System (LVAS; Abbott, Chicago, IL, Study Sponsor) showed a decrease in hemocompatibility related adverse events relative to the HeartMate II (HMII) LVAS (Abbott, Chicago, IL)⁵. This included decreases in pump thrombosis⁶, stroke⁷⁻⁹, and bleeding⁹ event rates. Despite these noted improvements a high residual risk of bleeding persists in patients treated with the HM3 LVAD⁹. Patients implanted with the HM3 pump are treated with a combination of antiplatelet and anticoagulation therapy but the role and implications of this regimen in determining the burden of hemocompatibility related adverse events have not been adequately investigated^{9,10}. Whether antiplatelet therapy is essential in concert with anticoagulation in treating such patients remains unknown.

This clinical investigation is a prospective, randomized, double-blinded, placebo-controlled study of advanced heart failure patients treated with the HM3 with two different antithrombotic regimens: vitamin K antagonist with aspirin versus vitamin K antagonist with placebo. The objective of this investigation is to study the safety and efficacy of an anti-platelet-free antithrombotic regimen in patients with advanced heart failure treated with the HM3 LVAS.

This clinical investigation will be conducted in accordance with this clinical investigation plan (CIP). All investigators involved in the conduct of the clinical investigation will be qualified by education, training, or experience to perform their tasks and this training will be documented appropriately.

1.1 **Background and Rationale**

1.1.1 **Background**

The CE Mark trial (clinicaltrials.gov identifier: NCT02170363) for the HM3 LVAD was a prospective, multicenter, single arm trial that enrolled 50 subjects at 10 sites. Six-month outcomes from this trial demonstrated 92% (confidence interval 83-97%) survival and led to the CE Mark approval of the HM3. Analysis of longer term data demonstrated a 2-year survival of $74 \pm 6\%$ ¹¹. No instances of device thrombosis were observed in this cohort at 2 years¹¹. Subjects will be followed through 5 years as a condition of CE Mark approval.

After approval, the ELEVATE (Evaluating the HeartMate 3 with Full MagLev Technology in a Post-Market Approval Setting; clinicaltrials.gov identifier: NCT02497950) registry was initiated to collect real-world data (i.e. there were no enrollment criteria) on consecutive HM3 patients at 26 total centers in Europe, Israel, Singapore, and Kazakhstan. The study enrolled 463 primary implant patients, 19 pump exchange patients, and collected only outcome data on an additional 58 patients who were unable to provide consent due to a study outcome (n=57 death, n=1 explant). The ELEVATE trial reported, for the primary implant cohort at 2-years, actuarial survival of 83.4%, and adverse events of stroke in 10%, suspected pump thrombosis in 1.5%, and bleeding in 34%¹².

Clinical Investigation Plan

The MOMENTUM 3 study (clinicaltrials.gov identifier: NCT02224755) was a prospective, randomized, multicenter, non-blinded, clinical trial that enrolled 1,028 patients at 69 sites in the US. The study randomized patients to receive either the HM3 or HMII LVAD. The study design incorporated an initial safety phase that evaluated 30 subjects at 5 sites prior to study expansion¹³. The primary objective of the trial was to evaluate the safety and efficacy of using the HM3 LVAD in indicated patients at two timepoints: 6 months (short-term n=294) and 2 years (long-term n=366)¹³. The primary endpoint was a composite of survival free of disabling stroke or survival free of reoperation to replace or remove the device (for reasons other than recovery)¹⁴. The secondary endpoint, which the study was powered to assess, was freedom from pump exchange through 2-years of follow-up in the full cohort of 1028 patients. All study endpoints were successfully met^{6,8,9}. The MOMENTUM 3 trial reported the full cohort HM3 actuarial survival at 2-years as 79.0% and stroke rates of 9.9%, suspected pump thrombosis rates of 1.4%, and bleeding rates of 43.7%⁹. An analysis of the burden of hemocompatibility related adverse events showed improved survival free of hemocompatibility related adverse events with the HM3 over the HMII at 6 months⁵ and 2 years¹⁵. Within the full cohort HM3 arm of MOMENTUM 3, at all time points, a cohort of patients were noted without aspirin as a part of their anti-thrombotic regimen, specifically at 6-months n=72/446 (16%), at 1-year n=78/371 (21%), at 18-months n=73/314 (23%), and at 2-years n=64/286 (22%)⁹. The MOMENTUM 3 study will continue to follow patients through 5-years post-implant as a condition of approval. After full enrollment in the MOMENTUM 3 study, a single arm (HM3 only) continued access protocol (CAP) was initiated while the MOMENTUM 3 IDE patients were being followed. This CAP study enrolled 1685 patients who will be followed for 2 years post implant.

A single center in Europe has investigated the use of the HM3 with low intensity anticoagulation (INR 1.5-1.9) in select patients, and reported positive outcomes¹⁰. These outcomes lead to the full removal of anticoagulation therapy in a subset of the low intensity anticoagulation patients, with favorable outcomes¹⁶. Additionally two reports from Europe have emerged on their initial experience with warfarin monotherapy with the HM3^{17,18}. Both studies conclude it may be safe to remove aspirin therapy from HM3 patients and called for further evaluation of the effects of discontinuation of aspirin in HM3 patients. Specifically, in a multicenter, retrospective, observational study performed at the San Raffaele Scientific Institute in Milan and A.O. Brotzu in Cagliari, Italy, patients were stratified based on bleeding risk; patients with a HAS-BLED score ≥ 4 or who experienced a post-operative bleeding event were considered high risk¹⁷. Patients at high bleeding risk were discharged on warfarin monotherapy with INR targeted to 2.0-2.5 whereas the remaining patients were discharged with warfarin (INR 2.0-2.5) and aspirin (100mg/day) antithrombotic therapy¹⁷. In the other study at the University Hospital Birmingham, United Kingdom, a retrospective analysis of a prospective audit of a change in their institutional standard of care was conducted¹⁸. The center implemented as standard of care the discontinuation of aspirin therapy after >3 months or following a bleeding complication.

1.1.2 Rationale for Conducting this Clinical Investigation

Patients implanted with LVADs are typically treated with a combination of antiplatelet and anticoagulant therapy but the role and implications of this regimen in determining the burden of hemocompatibility related adverse events in patients implanted with the HM3 LVAS have not been adequately investigated^{9,10}. Furthermore, a recent study showed that aspirin, in older, healthy adults without an LVAD, was associated with increased risk of major bleeding, including upper gastrointestinal bleeding, without a reduction in thromboembolic events including ischemic stroke¹⁹. Whether antiplatelet therapy is essential in concert with anticoagulation in treating LVAD patients remains unknown.

Clinical Investigation Plan

Hemocompatibility related adverse events, both thrombotic and hemorrhagic, are highly interrelated. Frequently changes to a patient's antithrombotic therapy that occur in the setting of hemocompatibility related adverse events increase the propensity toward opposing events. Specifically, treatment of a thrombotic event with additional antithrombotic intensity may result in a hemorrhagic event or vice-versa. While these events may be commonly discussed discretely, decoupling them in the setting of a patient population predisposed to both events is not possible, which can lead to difficulty interpreting the results of clinical studies or, in the worst-case scenario, studies with little or no interpretive value. As such, this study focuses on de novo LVAD implants and the first events, prior to such modifications to the treatment arm antithrombotic regimen while encouraging investigators to maintain the randomized treatment arm therapy as long as clinically permissible, in an effort to avoid such confounding factors.

Bleeding events with the HM3, while decreased in comparison to a predicate device, remain burdensome⁹. All major prospective clinical trials conducted with the HM3 (MOMENTUM 3, CE Mark) have been in the context of a prescribed antithrombotic regimen of aspirin in concert with vitamin K antagonist. Within clinical studies^{9,10,16}, as institutional changes to their standard of care¹⁸, or in response to increased bleeding risk¹⁷, modifications to the HM3 anticoagulation regimen have been explored. Prior to the introduction of the HM3, which has a decreased thrombotic profile relative to the HMII, studies investigating the need for aspirin within the HMII antithrombotic regimen were conducted²⁰⁻²³. The experience with the HMII, the improved outcomes with the HM3 and the early experience of single centers exploring modification to the antithrombotic regimen in HM3 patients provide evidence for the clinical equipoise in HM3 antithrombotic therapy and forms the basis for randomization of patients to aspirin (100mg) vs placebo arms within this trial.

2.0 CLINICAL INVESTIGATION OVERVIEW

2.1 Clinical Investigation Objective

To study the safety and efficacy of an anti-platelet-free antithrombotic regimen in patients with advanced heart failure treated with the HM3 LVAS.

2.2 Hypothesis

Withdrawal of antiplatelet therapy from the antithrombotic regimen of HM3 pump patients will not adversely affect safety or efficacy of the HM3 and may reduce non-surgical bleeding.

2.3 Device(s) To Be Used in the Clinical Investigation

This Clinical Trial investigates the treatment of advanced heart failure with the HM3 and if the use of antiplatelet therapy is required as part of the antithrombotic regimen. Refer to the HM3 Instruction for Use (IFU) in your country for additional details.

Clinical Investigation Plan

[REDACTED]	[REDACTED]	[REDACTED]	[REDACTED]	[REDACTED]
[REDACTED]	[REDACTED]	[REDACTED]	[REDACTED]	[REDACTED]

[REDACTED]

[REDACTED]

[REDACTED]

[REDACTED]

[REDACTED]

Clinical Investigation Plan

A series of horizontal black bars of varying lengths and positions on a white background, suggesting redacted text. The bars are irregular in length and position, creating a stepped effect across the page. There are approximately 10-12 such bars.

2.4 Treatment Arm Medication

2.4.1 Project Management

Clinical Investigation Plan

[REDACTED]

[REDACTED]

[REDACTED]

[REDACTED]

[REDACTED]

[REDACTED]

2.4.2 Treatment Arm Blinding

This study shall use 100mg aspirin, blinded against a placebo-to-match. Sites should reach out to the sponsor immediately regarding unblinding questions.

2.4.3 Treatment Arm Bottle Dispensing

Initial dispensing of the treatment arm bottle will occur upon randomization. Subjects will begin taking the treatment arm medication within 24 hours of randomization. Subjects will be resupplied 1 bottle at Month 3, Month 6, and Month 9 follow-up visits and 2 bottles at month 12 and every 6 months thereafter until study closure.

[REDACTED]

[REDACTED]

[REDACTED]

Subjects should always be sufficiently supplied with treatment arm medication until their next resupply visit. Each bottle will contain 120 capsules of the treatment arm medication, which is a sufficient supply for the period leading up to the subject's next visit, including the acceptable visit windows. Sites should carefully schedule follow up visits to ensure subjects are always sufficiently supplied.

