2.4.4 Antithrombotic Therapy

Antithrombotic therapy throughout the study should consist of a vitamin K antagonist (e.g. warfarin, fluindione, phenprocoumon, etc.) and the treatment arm medication. No additional anti-platelet agents

Clinical Investigation Plan

will be added while patients are on the treatment arm medication. The treatment arm medication will be taken once daily by mouth. Vitamin K antagonist therapy will be per standard of care (SOC) with a target INR of 2.0-3.0. The use of aspirin and a vitamin K antagonist is normal clinical practice at many centers and is part of the HM3 IFU.

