2.4.5 Treatment Arm Medication Accountability

To ensure treatment arm medication accountability, all bottles including (if applicable) all unused doses will be returned to ALMAC Clinical Services by the site. Subjects will be instructed to return the bottle and any unused doses of the treatment arm medication at each resupply visit.

The bottles and unused doses will be shipped (at the Sponsor's expense) per country- or region-specific Treatment Arm Medication Accountability Return Instructions.

In the event that a site has several bottles or unused portions to return to ALMAC Clinical Services, return shipments may be combined into a batch shipment. Empty research bottles and unused doses should not be stored on site and should be shipped to ALMAC Clinical Services within 14 days of receipt from the subject. Treatment Arm Medication Accountability Return Instructions will be provided during training.

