6.3 Study Activities and Procedures

The assessments in table 2 will occur throughout the study.

Table 2 – Schedule of Assessments

Assessment	Baseline	Implant	Randomization	Discharge	Week 1 (\pm 3 days)	Month 1 ¹ (\pm 7 days)	Month 3 ¹ (\pm 30 days)	Month 6 ¹ (\pm 30 days)	Month 9 ¹ (\pm 30 Days)	Month 12 ¹ (\pm 30 days)	Every 6 months \pm 60 days thereafter	As Occurs/ Unscheduled
Inclusion/ Exclusion	X	X										
Informed Consent	X											
Demographics	X											

Clinical Investigation Plan

Assessment	Baseline	Implant	Randomization	Discharge	Week 1 (± 3 days)	Month 1 ¹ (± 7 days)	Month 3 ¹ (± 30 days)	Month 6 ¹ (± 30 days)	Month 9 ¹ (± 30 Days)	Month 12 ¹ (± 30 days)	Every 6 months ± 60 days thereafter	As Occurs/ Unscheduled
General and Cardiac Medical History	X											
Coagulation Assessment	X ⁴											
Right Heart Catheterization	X ²											X ⁴
Modified Rankin Score (MRS)	X											X
Incidental Use of Aspirin Containing Products	X			X	X	X	X	X	X	X	X	
Vital Signs	X			X	X	X	X	X	X	X	X	X
Laboratory Assessments	X ³				X	X	X	X	X	X	X	X ⁴
Anticoagulation/Antiplatelet Medications Log	X	X		X	X	X	X	X	X	X	X ⁹	X
Echocardiogram	X ²				X ⁴	X ⁴	X ⁴	X ⁴	X ⁴	X ⁴	X ⁴	X ⁵
Other Medications	X					X	X	X	X	X	X	X
Sample for Core Lab (ASA response, US only)	X						X	X		X		
QOL and Functional Capacity	X						X	X		X		
Implant Data		X										X ⁶
Enrollment	X ⁷											
Randomization			X									
Pump Parameters		X			X	X	X	X	X	X	X	X ⁵
Bottle Requisition via WebEZ			X				X	X	X	X	X	X ⁸
Bottle Dispensing/Return Log			X				X	X	X	X	X	X ⁸
Return Used Bottle to ALMAC for Accountability							X	X	X	X	X	X ⁸
Initial Discharge Data				X								
Cardiac Arrhythmias Assessment (e.g. EGM, EKG)	X				X	X	X	X	X	X	X	X
Subject Status					X	X	X	X	X	X	X	X ⁸
INR & LDH Log	X			X	X	X	X	X	X	X	X	X
Death												X
Withdrawal (early termination)												X
Transition to Open Label												X
Hospitalizations												X
Adverse Events												X
Device Deficiencies												X
Operative Procedures (excluding primary implant)												X

¹ For follow-up visit scheduling, one month = 30 days.

² Most recent results within 30 days prior to implant, if collected as SOC.

³ Most recent results obtained within 30 days prior to implant will be permitted as baseline data.

⁴ If performed as SOC.

⁵ At time of suspected thrombotic adverse event or pump exchange, if performed as SOC.

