6.8 Scheduled Follow-up for All Subjects

The required assessments (detailed in tables 2 and 6), follow-up schedule, and associated visit windows (table 5) are generally aligned with SOC LVAD patient follow up and MCS registry data collection. All follow-up visits are based on the initial implant date. The windows for each follow-up visit are as follows:

Table 5 – Follow-up Visit Windows

Randomization	Visit 1	Visit 2	Visit 3	Visit 4	Visit 5	Visit 6	Visit 7+
2-7 days	Week 1 ± 3 days	Month 1 ± 7 days	Month 3 ± 30 days	Month 6 ± 30 days	Month 9 ± 30 days	Month 12 ± 30 days	Every 6 Months ± 60 days

The follow-up visit must occur within the designated window. Follow-up assessments for a single visit do not have to occur on the same date, but must occur within the designated window, or will be considered a protocol deviation. The Sponsor understands that some lab results may be received several days after the visit has occurred, in these instances the date the lab occurred is considered as the date the blood draw occurred. All subjects should be asked, at each follow up visit after discharge, if they were seen at an outside facility. If so, medical records from any facility that has seen the patient must, with the subject's consent, be requested and reviewed for potential adverse events.

For subjects not on the treatment arm medication, the completion of the Month 12 visit will signify completion of the study, with the exception of some lab results that may be received after the visit has occurred, no other assessments or study related activities may be performed after the final visit has occurred, even if later assessments are performed within the acceptable window. Month 12 assessments (including required laboratory assessments blood draws) not collected by the date of the final visit will be considered protocol deviations.

Subjects on the treatment arm medication will continue to be followed every 6 months after their month 12 visit until the final ongoing patient completes their month 12 visit or experiences a study outcome. Upon close of enrollment, the sponsor will notify sites of the anticipated date of study conclusion which will be 12 months after the last patient enrolls. All required visit data must be collected by the final visit, as outlined above.

Clinical Investigation Plan

Table 6 – Scheduled Follow-Up Visit Data Collection through 12-months

Study Activity	Definition

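### A 120-capsule bottle does not cover the visit windows in Months 3 to 12 when an early visit is followed by a late one

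*Protocol*

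**What the plan says.** CIP 2.4.3 (Treatment Arm Bottle Dispensing) provides one bottle at randomization and one at each of Months 3, 6 and 9. It says of the bottle: "Each bottle will contain 120 capsules of the treatment arm medication, which is a sufficient supply for the period leading up to the". The end of that sentence extends the claim to the windows: "next visit, including the acceptable visit windows". The next sentence adds: "Sites should carefully schedule follow up visits to ensure subjects are always sufficiently supplied".

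Four other statements determine whether the supply claim is right:

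- Dosing, CIP 2.4.4: "The treatment arm medication will be taken once daily by mouth".
- Leftovers, CIP 2.4.5: "Subjects will be instructed to return the bottle and any unused doses of the treatment arm medication at each resupply visit".
- Anchor for visits, CIP 6.8: "All follow-up visits are based on the initial implant date", and "The follow-up visit must occur within the designated window". Table 5 sets the window at ±30 days for Months 3, 6, 9 and 12.
- Length of a month, CIP Table 2, footnote 1: "For follow-up visit scheduling, one month = 30 days".

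Table 2 also allows a bottle to be requisitioned at an unscheduled contact, and Table 6 refers to replacement bottles given outside the visit schedule. Several lines of 2.4.3 are redacted.

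**The concern.** The windows are counted from implant, so coming early to one visit does not bring the next window forward. An early visit lengthens the interval that the next bottle has to cover. Since leftover capsules are returned, nothing carries over. A subject can therefore attend every visit in window, with no deviation under 6.8, and still run out.

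The sentence about supply sits directly beside the instruction to schedule carefully, and it tells sites that the windows are already allowed for. A coordinator who relies on it has no reason to check the interval for the one pattern that fails.

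What is at stake is continuity of assigned drug. An aspirin-arm subject without capsules is treated like a placebo-arm subject, while a gap in placebo changes nothing. Gaps therefore make the arms more alike, which matters in principle for a non-inferiority comparison.

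**Working it through.** **Inputs.** Supply is 120 capsules per bottle (2.4.3). Dosing is once daily (2.4.4); one capsule per dose is my assumption, since the visible text gives no capsule count. With 30-day months (Table 2), nominal days are 90, 180, 270 and 360 from implant. Windows are ±30 days (Table 5). Randomization is on day 2 to 7 (5.5). There is no carry-over (2.4.5).

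**Where the plan's statement holds.**

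- Randomization to a late Month 3 visit: 120 − 2 = 118 days at most (113 if randomized on day 7). Covered.
- On-time visit to a late next visit: 90 + 30 = 120 days. Exactly covered.

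**Where it does not.** Longest in-window interval = (later nominal day + 30) − (earlier nominal day − 30):

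- Month 3 to 6: 210 − 60 = 150 days
- Month 6 to 9: 300 − 150 = 150 days
- Month 9 to 12: 390 − 240 = 150 days

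Each is 150 − 120 = 30 days short. In general, write each visit's offset as days after its nominal day (negative if early). Uncovered days = max(0, next offset − previous offset − 30).

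**Worst case over time.** Two adjacent intervals cannot both overrun: the first would need the shared visit to be late and the second would need it to be early. By day 360 the maximum is therefore 30 days. A bottle given on day 240, the earliest Month 9 visit, lasts through day 359, so every Month 9-12 shortfall falls on or after day 360. Offsets of −30, +30, −30, +30 leave days 180-209 and 360-389 uncovered, which is 60 days up to a Month 12 visit on day 390.

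**Expected size.** The documents give no distribution of visit days, so I assume one: independent whole-day offsets, every subject on drug to Month 12, no remedy applied.

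Uniform offsets give 61 × 61 = 3,721 equally likely pairs per interval. Pairs with a difference above 30 number 30 + 29 + … + 1 = 465, so 465/3,721 = 12.5% of intervals overrun. Total uncovered days over all pairs are Σ m(31 − m) for m = 1 to 30 = 4,960, so the mean is 4,960/3,721 = 1.33 days per interval. By day 360 only Months 3-6 and 6-9 count: 2 × 1.33 = 2.67 days. Since the two cannot both occur, 2 × 12.5% = 25% of subjects have a gap. Time on drug to day 360 is about 355 days, so 2.67/355 = 0.75%.

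The same enumeration with normal offsets is given below. Each range runs from truncating the distribution at the window to piling out-of-window visits on its edges.

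| Assumed spread | Intervals over 120 days | Uncovered days to day 360 | Subjects with a gap by day 360 |
|---|---|---|---|
| Uniform | 12.5% | 2.7 (0.75%) | 25% |
| SD 15 days | 5.3-6.9% | 0.8-1.2 (0.22-0.34%) | 11-14% |
| SD 10 days | 1.4-1.5% | about 0.15 (under 0.1%) | 3% |

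**Scale against the margin.** If dilution is roughly proportional to uncovered time, a true difference equal to the 10-point margin would shrink by about 10 × 0.0075 = 0.075 percentage points in the uniform case.

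**The case against.** The strongest reply is that 120 = 90 + 30. The bottle appears to be sized for the nominal interval plus the next visit's window, and on that reading the sentence is correct. This explains the figure, but the sentence speaks of windows without that restriction. Because visits are anchored to implant, the previous visit's window also affects the interval. The fault is an over-broad statement, not a miscalculated bottle size.

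A second reply is that the plan already deals with this. Sites are told to keep subjects supplied by careful scheduling, and bottles can be requisitioned outside the schedule. Both reduce the risk, and the figures above ignore them. Neither gives a visible interval limit, and both depend on someone noticing a gap that the preceding sentence says cannot arise.

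Third, the redacted lines of 2.4.3 may contain such a limit. That stands, so the point concerns the visible sentence only and does not say that the plan lacks a rule.

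Two stronger readings are tempting, but the documents do not support them. A reader might count all three intervals and infer 60 uncovered days within the first 360. The third interval's shortfall cannot begin before day 360, so that total applies only up to a late Month 12 visit. A reader might also infer from CIP 5.6 that any supply gap beyond 72 hours moves a subject to open label for good. That section concerns cessation by the investigator in response to clinical events, and the visible text does not say how a supply gap is classified.

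**Conclusion.** The sufficiency statement in CIP 2.4.3 is wrong for one in-window pattern: a visit before its nominal day followed by one far enough after its own that the two deviations together exceed 30 days. Up to 30 days can then go uncovered in an interval. The cumulative worst case is 30 days by day 360, or 60 days to a Month 12 visit on day 390. Both are given because SAP 2.3.1 judges success at the 12-month visit.

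The 150-day span follows directly from the visible rules. The shortfall also rests on one capsule per dose and on the return of leftovers. If subjects could keep leftovers, a Month 3 visit on day 60 would leave 62 to 67 capsules in hand, more than the 30 needed to reach a late Month 6 visit. The expected uncovered time, from about 0.15 to 2.7 days per subject by day 360, rests on assumed visit spreads with no remedy, so actual gaps should be smaller.

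Severity is minor. The likely effect on the trial's result is small, and nothing here calls the primary comparison into question. The point is limited to Months 3 to 12.

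**What to change.** Change 2.4.3 to say that one bottle covers 120 days of dosing. Unless the redacted lines already contain it, add one rule: from Month 3 to Month 12, consecutive resupply visits are booked no more than 120 days apart, or an unscheduled bottle is dispensed when the booked interval is longer.

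The cap always fits the existing windows. After a Month 3 visit on day 80, Month 6 can fall on days 150-200, which is 51 of the 61 window days. After the earliest visit, on day 60, it can fall on days 150-180, which is 31 days. The cost is a shorter window after an early visit, never under 31 days.

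The bottle option costs 628 subjects × 3 intervals × the share of intervals over 120 days: 628 × 3 × 0.125 = 235 extra bottles if visits are uniform, 101 to 130 at SD 15 and 27 to 29 at SD 10. Subjects who leave early would lower these.

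No visit, endpoint or analysis changes. Because CIP 10.3 requires documented IRB/EC acknowledgement or approval of each amendment, at up to 50 centers, the two sentences are best carried in the next planned amendment.
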